2.7. Required training and experience

On-site initiation visits will be organized, in which full training will be given to all appropriate staff members participating in the clinical investigation, including principal investigators, study coordinators and any other site personnel pivotal to the conduct of the clinical investigation. This training will include at least the following: instructions on the functions and use of the investigational device by the Sponsor, training on SBSS for assessment of bleeding at the target site, procedures outlined in the clinical investigation plan, main principles of Good Clinical Practices for Medical Devices (ISO 14155), instructions on completion of the case report forms, content of the investigator site file, and management of device deficiencies.

2.7.1. Surface Bleeding Severity Scale (SBSS)

DHF-01-QR-021	Page 23 of 62	Version 04, 28 April 2021
Confidential		GATT Technologies BV

The investigators at each site will have training on the SBSS prior to the enrollment of any subjects. Training will be in conformity with the certified e-learning training set up by the SBSS developer and owner [1]. Training on the SBSS will be performed to reduce intra-rater variability in the assessment of bleeding at the target site. A training record will be signed on completion of the training and filed in the TMF.

2.7.2. Investigational Device and Procedure

All investigators will have extensive training on the investigational device prior to the start to reduce a potential influence of a learning curve in using the device on outcome. A training record on the investigational device training will be signed on completion of the training and filed in the TMF. The principal investigator will get acquainted with use of the device during implantation in animals, after which they can use GATT-Patch on trial subjects. Each additional surgeon that has not yet used GATT-Patch will be proctored by the principal investigator or an experienced investigator that has previously used GATT-Patch at least once. The flow of training by proctoring is further explained in Figure 2-3. A training record for the proctoring session will be signed on completion of the training and filed in the TMF.

FIGURE 2-3: GATT-PATCH TRAINING FLOWCHART

PI = principal investigator; numbers reflect additional surgeons performing surgery with GATT-Patch

2.7.3. Qualifications

The investigators will have adequate qualifications with regards to the following:

- trained on use of GATT-Patch;
- trained on the SBSS;
- trained in performing specific surgical procedures;
- experience and training in clinical studies, particularly clinical studies involving medical devices, and Good Clinical Practices for Medical Devices (ISO 14155);
- able to read and understand English.

2.8. Device traceability

Investigational devices used in this clinical investigation will be labelled with a unique LOT number. The unique LOT allows for identification and tracking of devices throughout the clinical investigation. The devices will be labelled with the text "Exclusively for Clinical Investigation" to avoid non approved use of the device. Further details are provided in Section 10. In addition, the patient card further ensures the identification of the device and continued traceability after study termination.

DHF-01-QR-021
Confidential

Page 24 of 62

3. JUSTIFICATION FOR CLINICAL INVESTIGATION DESIGN

3.1. Pre-clinical testing

GATT Technologies BV performed pre-clinical testing to assess residual risks associated with the device. Details on pre-clinical testing are provided in the Investigator Brochure (DHF-01-SFT-164). Design verification and validation was performed in accordance with national and international standards. The outcomes of the pre-clinical tests demonstrated that the device performs as intended and is safe for use in humans.

3.2. State of the art

This first-in-human clinical investigation will generate the first clinical data for GATT-Patch. A literature review was performed to establish clinical evidence referring to the clinical safety and performance, and associated risks and benefits of GATT-Patch (Literature Review Protocol Version 01, 24 September 2020). The objective was to identify comprehensive and up-to-date information on established therapies, the safety and performance of state-of-the-art treatments and/or devices, methods to assess effectiveness, and known adverse events that are related to the management of hemorrhage during liver surgery. Relevant outcomes included adverse events, device deficiencies, study population (eligibility criteria), primary effectiveness/performance and safety outcome measures and secondary outcome measures. Overall, data obtained through the literature review was used to provide input to the assessment of acceptable benefit/risk profiles of GATT-Patch and to determine the performance goal for the proposed clinical investigation on GATT-Patch. A summary is provided below. Detailed results are provided in a Literature Review Report (DHF-01-SFT-166, Version 01).

There are numerous hemostasis and sealing products approved for bleeding during surgery (Table 2). This includes both biological and synthetic products as well as patches and non-patches. These products have different modes of action based on their composition, but despite differences in composition and formation (patch vs non-patch), many of these products have a similar indication as adjunct to hemostasis. These products are thus relevant to consider as alternatives to GATT-Patch.

For the risk management activities, specific alternative patches that are approved for hemostasis in Europe, such as TachoSil, Veriset, and HEMOPATCH and that have a similar mode of action and intended use as GATT-Patch were used to provide input in the risk profile of GATT-Patch. The clinical evaluation will further elaborate on current alternative treatment options that have the same indication as GATT-Patch.

Group	Category	Class	
Hemostats Mechanical Porcine gelatin		Porcine gelatin	
		Bovine collagen	
		Oxidized Regenerated Cellulose (ORC)	
	Active	Bovine thrombin	
		Human-pooled plasma thrombin	
		rhThrombin	
	Combined	Porcine gelatin + thrombin	
		Bovine gelatin and human-pooled plasma thrombin	
Hemostatic	Fibrin Sealants	Human plasma and human thrombin	
Sealants		Human-pooled plasma and bovine thrombin	

TABLE 2: ALTERNATIVE HEMOSTATIC (AND SEALING) AGENTS

DHF-01-QR-021 Confidential Page 25 of 62

Group	Category	Class
		Individual human plasma, bovine collagen and bovine thrombin
		Human-pooled plasma and equine collagen
	Synthetic sealants,	Two PEGs
	PEG-based	PEG, trilysine amine and FD&C blue #1
		PEG and human serum albumin
	Albumin and	Bovine serum albumin and 10% glutaraldehyde
	glutaraldehyde	

In general, topical hemostatic agents have been found effective to control bleeding at bleeding sites that include raw diffuse bleedings and that are difficult to control using traditional hemostatic techniques [2, 3]. GATT-Patch is intended to provide fast and persistent control of bleeding during surgeries on internal organs, as well as robust adhesion and sealing. When compared to other hemostatic agents that are considered standard of care or when compared to benchmark devices, it is expected that GATT-Patch will provide at least the same rate of hemostasis but faster and with improved adhesion for a prolonged benefit. The flexibility and pliability of GATT-Patch allows it to be used in a variety of clinical situations where current standard-of-care patch products are impractical for use. Furthermore, the composition and mode of action of GATT-Patch differentiates from currently approved products and thereby addresses the medical need of a combination of quick hemostasis, persistent hemostasis, and strong adhesion and tissue sealing.

The risks of GATT-Patch are considered similar to other hemostasis and sealing devices used during liver surgery (patch and non-patch). There is low risk of adverse events associated with topical hemostatic agents [3]. Device-related adverse events (AEs) that were identified for benchmark devices (devices with similar properties and the same intended use as GATT-Patch) occurred with a low incidence rate: 0-18.2%, with 18.2% being a reported imbalance in treatment assignment to two investigators, who had a different interpretation of causal events than other investigators. If not taken into account, device-related AE occurred in a range of 0-6.7% and included the risk of bile leak, hematoma, anemia, diarrhea hypomagnesemia, localized intra-abdominal fluid collection, nausea, peritoneal abscess, pleural effusion, infectious peritonitis, liver abscess, postoperative abscess, postoperative adhesion and procedural hemorrhage. There is no risk of immunogenicity. One device-related event of increased C-reactive protein was identified (1.8%) but was not considered non-serious.

The present clinical investigation is intended to investigate whether the device is safe and performs as intended when compared to the state of the art. It is hypothesized that (1) a high rate of hemostasis, (2) a short time to hemostasis, and (3) persistent hemostasis results in less intraoperative and postoperative risk to patients undergoing these surgeries.

3.3. Clinical development stage

This clinical investigation is intended to collect clinical safety and performance data for CE-mark of the device in Europe. In addition, the results will be used for the design of an investigational device exemption (IDE) trial and commercialization in the US.

Page 26 of 62

3.4. Justification

Clinical data from competitor devices and standard of care treatment for open liver surgery were reviewed and were used to predict safety and performance outcomes of GATT-Patch and to create appropriate preventive measures for possible risks associated with the device. All residual risks for GATT-Patch have been assessed and reduced to an acceptable or tolerable level. The clinical investigation is performed to evaluate clinical safety and performance of the device for use in open liver surgery. The primary objective is to meet the general safety and performance requirements for GATT-Patch as intended for its CE marking in Europe as they relate to safety and performance and acceptability of the benefit-risk profile.

4. RISKS AND BENEFITS OF THE INVESTIGATIONAL DEVICE, CLINICAL PROCEDURE AND CLINICAL INVESTIGATION

4.1. Anticipated clinical benefits

The intended clinical benefit of GATT-Patch is to provide fast and persistent hemostasis during surgeries on internal organs, primarily parenchymatous organs such as liver, spleen or kidney; or in other abdominal surgeries. It is hypothesized that a high rate of fast and persistent hemostasis may result in less clinical risk of complications to patients undergoing these surgeries.

4.2. Anticipated adverse device effects & residual risks

Possible risks for GATT-Patch were assessed and controlled using the EN-ISO 14971 "Medical devices – application of risk management to medical devices". The results of the risk management are recorded in the risk management report (DHF-SFT-121). According to the results of the use risk assessment, the following risks are judged as 'tolerable and improbable to occur', as 'tolerable and remote to occur', or 'tolerable and occasional to occur':

- Toxic response
- Thromboembolic event
- (Re)Bleeding
- Allergic reaction
- Pain
- New surgery
- Infection
- Blockage of artery or vein / ischemia of organs
- Damage of organs and vessels
- Pulsatile hematoma
- Closing of intestinal track
- Biloma

Furthermore, the risk for encapsulated or rolled-up device was identified during the risk management, at a lower risk level/incidence. This risk will be further investigated in this clinical investigation by means of the 6-weeks follow-up imaging.

There were no risks identified as 'probable' or 'frequent' to occur, neither at a 'not acceptable' risk level.

Note: these events can be considered procedure- or device-related events. Adjudication will be based on the definitions provided in Section 13.

4.3. Risks associated with participation in the clinical investigation

The risks that are anticipated for participation in the clinical investigation are:

- Anticipated adverse device effect for the use of GATT-Patch as provided in Section 4.2.
- Procedure-related adverse events during open liver surgery similar to the standard of care.

Page 28 of 62

4.4. Risk control/mitigation

GATT Technologies BV performed risk analysis in accordance with EN ISO 14971:2019. All residual risks have been controlled and are mitigated to an acceptable level. Careful definitions of specific eligibility criteria, study procedures and instructions for use (DHF-01-QR-008), appropriate selection, qualification and training of the investigators, and patient follow-up procedures have been designed as to further contribute to reduce risks as far as possible for the patient and residual risk acceptance.

For the purpose of risk control and mitigation during the conduct of the study the clinical investigation will be split into 2 stages:

- **Stage I** of the clinical investigation will enroll a small cohort of subjects within which the initial safety of GATT-Patch will be evaluated. A maximum of 12 subjects (~25% of the overall population) will be treated⁸ at a maximum of 3 sites, after which the enrollment into the clinical investigation will be paused. At minimum, 2 subjects shall be treated per site.
- **Stage II** of the clinical investigation will enroll subjects until 39* Stage II subjects have been treated with the investigational device. (*Note: The number of Stage II subjects may increase to a maximum of 61 treated subjects [56 evaluable Stage II subjects, assuming 7.5% drop-out rate] if a sample size increase is deemed necessary based on the interim sample size reestimation). Stage II will be used to evaluate safety and performance of GATT-Patch.

Furthermore, potential risks associated with participation in this investigation will be minimized and managed in accordance with ISO 14155, and requirements of the approving Ethics Committee(s).

4.5. Benefit-risk rationale

GATT Technologies BV believes that any potential risk presented by this clinical investigation has been minimized and that adequate testing, safeguards, and safety monitoring have been incorporated into the clinical investigation to further minimize and mitigate the risks. GATT Technologies BV believes that the benefits of GATT-Patch outweigh the potential risks posed to participating subjects. This clinical investigation has been designed to involve as little pain, discomfort, fear and any other foreseeable risks as possible of the subjects. The risk threshold and degree of distress to subjects are defined in the risk analysis.

⁸ Treated subjects include subjects that are actually implanted with the device, or had a treatment attempt with the device.

5. OBJECTIVES, HYPOTHESES AND ENDPOINTS

5.1. Primary objective & hypothesis

To primary objective is to evaluate the clinical safety and performance of GATT-Patch in open liver surgery.

It is expected that GATT-Patch will achieve hemostasis within a specified time frame in the majority of patients and having a good safety profile. Statistical criteria for acceptation or rejection of the hypothesis are provided in Section 7.1.

5.2. Primary endpoint

The primary performance endpoint is defined as non-inferiority of GATT-Patch compared to the standard of care regarding the percentage of cases achieving hemostasis at 3 minutes (i.e., demonstrate GATT-Patch is significantly greater than literature-based performance goal of 65.4%).

Hemostasis will be defined by a grade of 0 (None/Dry) on the Surface Bleeding Severity Score (SBSS). The SBSS provides a validated score for assessment of bleeding at the target site, and consists of 6 subscales (0=none, 1=minimal, 2=mild, 3=moderate, 4=severe; not immediately life-threatening, 5=extreme; immediately life threatening) [1]. Investigators will be trained on the assessment scale prior to the investigation to have consistent assessment of bleeding at the target site (Section 2.7).

Achievement of hemostasis will be verified every 30 seconds, starting from the time that GATT-Patch is positioned and pressure is initiated. If hemostasis has not been achieved after 5 minutes of application (SBSS 1-5), then treatment is considered a failure and additional hemostatic agents or techniques may be used.

5.3. Secondary objectives & hypotheses

The following secondary endpoints are defined:

- Mean time to hemostasis (seconds)
- Percentage of hemostasis at 30, 60, 90, 120 and 150 seconds

There will be no formal hypothesis testing on the secondary performance endpoints.

5.4. Safety objective and safety endpoints

The safety of GATT-Patch will be assessed by the nature, severity and incidence of device related adverse events. The adverse events found for GATT-Patch will be compared to the current knowledge and state of the art for hemostatic methods in open liver surgery to assess whether the device is associated with acceptable safety outcomes.

Adverse events may include:

- Toxic response
- Thromboembolic event
- (Re)Bleeding
- Allergic reaction
- Pain
- New surgery
- Infection

DHF-01-QR-021 Confidential Page 30 of 62

- Blockage of artery or vein / ischemia of organs
- Damage of organs and vessels
- Pulsatile hematoma
- Closing of intestinal track
- Biloma
- Encapsulated or rolled-up device

No formal hypothesis testing will be performed for the safety objective and endpoint of this clinical investigation.

5.5. Exploratory endpoints

In addition to the primary endpoint, the following exploratory endpoints will be recorded:

- Surgery Time (minutes)
- Blood loss (mL) during surgery
- Blood Transfusion (mL) during hospitalization
- SBSS (0-5) at the target bleeding site
- Use of adjunct hemostatic agents/techniques (e.g. cautery, sutures or staples)
- Amount of material needed versus bleeding surfaces
- User satisfaction (questionnaire)

5.6. Rationale for endpoint selection

Endpoints were selected based on outcomes reported for other topical hemostatic agents in the scientific literature. The meta-analysis described in Section 3.2 identified 15 articles reporting on hemostatic techniques during open liver surgery, and this included 6 articles that specifically reported on the percentage of hemostasis at 3 minutes [4, 8-12]. Percentage of hemostasis at 3 minutes was found a clinically relevant performance outcome for success of various hemostatic techniques during open liver surgery. Data from different studies and techniques were pooled to define a performance goal for GATT-Patch to be used in the sample size calculation (Table 3). Detailed results per article are provided in a Literature Review Report (DHF-01-SFT-166, Version 01). The performance goal of GATT-Patch is based on the lower bound of the pooled rate of hemostasis at 3 minutes.

TABLE 3: SUMMARY OF PRIMARY ENDPOINT OUTCOME REPORTED IN SCIENTIFIC LITERATURE AND USED IN SAMPLE SIZE CALCULATION

Reference	Group	N	Time to hemostasis #	Hemostasis at 3 min
6 RCTs	TachoSil, ORC (Surgicel), Sangustop, Veriset, Grifols, Fibrocaps, Gelatin sponge (Gelfoam or Spongostan)	799 patients	Range: 1 min- 5.5 min	Weighted average: 74.8% (95% Cl: 65.4% to 83.1%)

Page 31 of 62

6. DESIGN OF THE CLINICAL INVESTIGATION

6.1. General

This is a pre-market, prospective, single arm, multicenter first-in-human clinical investigation.

The clinical investigation will be split into 2 stages:

- Stage I of the clinical investigation will enroll a small cohort of subjects within which the initial safety of GATT-Patch will be evaluated. A maximum of 12 subjects (~25% of the overall population) will be treated⁹ at a maximum of 3 sites, after which the enrollment into the clinical investigation will be paused. At minimum, 2 subjects shall be treated per site. A DMC will review safety in this subset of subjects and decides whether the study may proceed (Section 13.8)
- **Stage II** of the clinical investigation will enroll subjects until 39* Stage II subjects have been treated with the investigational device. (*Note: The number of Stage II subjects may increase to a maximum of 61 treated subjects [56 evaluable Stage II subjects, assuming 7.5% drop-out rate] if a sample size increase is deemed necessary based on the interim sample size reestimation). Stage II will be used to evaluate safety and performance of GATT-Patch.

In both Stage I and Stage II, subjects will follow the same clinical investigation pathway. Stage I subjects will be analyzed for safety only, whereas Stage II subjects will be analyzed for both safety and performance.

6.2. Investigational device and comparators

This is an uncontrolled clinical investigation. Subjects will be treated with GATT-Patch (5x10cm).

6.3. Subjects

The clinical investigation will enroll subjects that are candidate for elective open liver surgery.

6.3.1. Inclusion criteria

- Subject is scheduled to undergo an elective open surgery on the liver;
- Subject is willing and able to give written informed consent for investigation participation;
- Subject is 18 years of age or older at the time of enrollment;
- Subject has been informed of the nature of the clinical investigation.

A subject must meet all of the following intraoperative inclusion criteria to be treated with the investigational device:

- Subject in whom the Investigator is able to identify a target bleeding site at the liver resection plane for which any applicable conventional means for hemostasis (e.g. suture, ligature or cautery) are ineffective or impractical and the choice is made to use a topical hemostat for control of hemostasis;
- Subject has a target bleeding site with a SBSS of 1, 2, or 3.

⁹ Treated subjects include subjects that are actually implanted with the device, or had a treatment attempt with the device.

6.3.2. Exclusion criteria

A subject must not meet any of the following pre-operative exclusion criteria to be enrolled into the clinical investigation:

- Subject is scheduled to undergo surgery on other organs besides the liver (e.g. pancreas, colon, lungs);
- Subject is taking multiple antithrombotic therapies in therapeutic dosage up to the time of surgery, allowing exclusive use of acetylsalicylic acid;
- Subject has platelet count <100 x 10⁹/L, an activates partial thrombin time of >100s, or international normalized ratio >2.5;
- Subject is pregnant, planning on becoming pregnant or actively breast-feeding during the follow-up period;
- Subject has a known hypersensitivity to brilliant blue (FD&C Blue #1);
- Subject has an active or suspected infection at the surgical site;
- Subject has a total bilirubin level of ≥ 2.5 mg/dl;
- Subject has had or has planned to receive any organ transplantation;
- Subject has American Society of Anesthesiologists (ASA) classification of 4/5;
- Subject has a life expectancy of less than 3 months;
- Subject has a documented severe congenital or acquired immunodeficiency;
- Subject in whom the investigational device will be used at the site of a synthetic graft or patch implant;
- Subject is currently participating or has participated in another clinical investigation within the past 30 days that may affect the endpoints of the study, such as trials related to the surgical procedure, and on anti-coagulation;
- Subject is not appropriate for inclusion in the clinical investigation, per the medical opinion of the Investigator;
- Subject has any incidental (pre- and peri-operative) findings deemed by the Investigator to potentially jeopardize the safety or welfare of the patient.

6.3.3. Representativeness of included population

This clinical investigation will enroll subjects that are candidate for open liver surgery. Subjects with an appropriate bleeding site (SBSS of 1, 2, or 3) will be treated with GATT-Patch. Therefore, the included population is considered a representative sample for the intended use of GATT-Patch.

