2.2. GATT-Patch

GATT-Patch (Figure 2-1) is a resorbable hemostatic sealing patch, contained in a sterile blister pack within a pouch, for topical use in internal surgery. It does not require freezing or other special storage requirements. It presents as a blue, soft, flexible, gelatin fiber-based carrier impregnated with an NHS-POx / NU-POx granulate. The dimensions of GATT-Patch are 50x100mm. As GATT-Patch is a homogenously impregnated fibrous material, both sides are active and it is also suited to being torn into smaller pieces for application in irregularly shaped structures and areas that are difficult to access with a larger item.

FIGURE 2-1: GATT-PATCH

GATT-Patch will be applied onto the wound site where the flexible and resorbable gelatin patch via contact activation starts the coagulation cascade, further enhanced by dehydrating the blood to concentrate the blood's solid elements leading to a matrix for platelet aggregation and release of coagulation factors enabling fibrin formation 'trapped' in the gelatin fibers. Once the patch is activated, via the combination of P(EtOx-OH-NHS), P(EtOx-NH2) and gelatin, a POx-hydrogel is formed. This POx-hydrogel has two effects: firstly, to adhere the patch to the tissue and secondly to form a seal across the damaged tissue. Both parts together help to ensure high efficacy hemostasis can be achieved.

GATT-Patch is a Class III Medical Device intended for application by trained physicians as an aid to hemostasis and sealing in internal organs during surgery after standard surgical hemostatic techniques have been applied. The effect is local and primarily mechanical and is not dependent on the coagulation status of the patient. The product is not removed at the end of surgery but is resorbed in 4-6 weeks⁷.

⁷ The resorption time was estimated 4-6 weeks based on initial preclinical testing of prototypes. The outcomes of a recent GLP implantation study on the final design of GATT-Patch shows resorption in <4 weeks.

2.2.1. Regulatory Classification

GATT-Patch is indicated for use as an adjunct to hemostasis and as a surgical sealant in surgery for minimal, mild or moderate bleeding sites. GATT-Patch is intended to be used for management of hemorrhage during surgeries on internal organs. GATT Patch will be totally introduced into the human body and intended to remain there after the procedure. It is fully degradable within 4-6 weeks.

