According to classification rule 8 of Annex VIII of the EU MDR 4 April 2017, the device is a long term surgically invasive and implantable device. The device will be wholly absorbed and it will undergo a chemical change in the body.

According to classification rule 18 of Annex VIII of the EU MDR 4 April 2017, the device is manufactured utilizing derivatives of animal origin, which are non-viable or rendered non-viable.

Therefore, according to both classification rules, GATT-Patch is classified as a Class III medical device.

2.2.2. Materials

A listing of the raw materials used in the manufacturing of the final finished P(EtOx-OH-NHS) - P(EtOx-NH2) granulate-based hemostatic patches is provided in Table 1. GATT-Patch is an implant, and all components are in direct contact with the human body.

Device Component	Raw Materials in Component	Supplier	CAS Number
Delumers	P(EtOx-OH-NHS) polymer	PolyVation	NA
Polymers	P(EtOx-NH2) polymer	PolyVation	NA
Blue Colorant FD&C Blue No. 1	FD&C Blue No.1	Spectrum Chem. via VWR	3844-45-9
Granulate	P(EtOx-OH-NHS) and P(EtOx-NH2)	GATT Technologies	NA
Porous Gelatin carrier (porcine origin)	Gelatin	Gelita Medical	9000-70-8

TABLE 1: RAW MATERIALS/CHEMICAL COMPONENTS GATT-PATCH

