2.3.2. Intended populations

The hemostatic sealant GATT-Patch will be intended for use in adult, adolescent and pediatric patients.

The final recommendations will depend on pre-clinical and clinical data, as the safety and performance of the device has not been yet established for use in specific populations as children, pregnant or lactating women.

It should not be used in patients with a known hypersensitivity to the component materials, including porcine proteins and brilliant blue (FD&C Blue No. 1).

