6.3.4. Definition of enrollment

A subject is considered enrolled in the clinical investigation after they have provided written informed consent, and if they meet the preoperative eligibility criteria (Section 6.3.1 and Section 6.3.2). The study will treat up to 73 subjects with the investigational device. Treated subjects include subjects that are actually implanted with the device, or had a treatment attempt with the device.

6.3.5. Randomization

N/A. This is a non-randomized clinical investigation.

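### The exclusion criteria carry over only brilliant blue, although section 2.3.2 also bars the device in known porcine-protein hypersensitivity

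*Protocol*

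**What the plan says.** Protocol section 2.3.2 (Intended populations) states of the device: "It should not be used in patients with a known hypersensitivity to the component materials, including porcine proteins and brilliant blue". Section 2.2.2 and its Table 1 give the composition, which includes a "Porous Gelatin carrier (porcine origin)", and add that "GATT-Patch is an implant, and all components are in direct contact with the human body". Section 2.2 says of the patch: "The product is not removed at the end of surgery but is resorbed in 4-6 weeks".

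The exclusion list in section 6.3.2 has one hypersensitivity item: "Subject has a known hypersensitivity to brilliant blue (FD&C Blue #1)". The synopsis repeats it. No other inclusion or exclusion criterion mentions porcine protein, gelatin, the polymers or component materials in general, and the SAP has no eligibility list of its own. Section 6.3.4 counts a consented subject as enrolled "if they meet the preoperative eligibility criteria (Section 6.3.1 and Section 6.3.2)"; it does not refer to 2.3.2.

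**The concern.** The protocol sets a bar on use in one place and transfers only half of its named content to the list that decides who enters the trial. A site working from 6.3.2 could reasonably infer that dye allergy is the only hypersensitivity that excludes.

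Patient safety is at stake. Section 4.2 lists "Allergic reaction" among the anticipated device risks, and section 4.4 relies on eligibility rules as one means of reducing risk: "Careful definitions of specific eligibility criteria, study procedures and instructions for use (DHF-01-QR-008)". The patch is a first-in-human implant that stays in the body after closure. A hypersensitivity already known before surgery is best acted on at screening through a named criterion.

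**Working it through.** No formula applies; this is a comparison of texts.

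**Step 1. What each place covers**

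| Material (Protocol Table 1) | Section 2.3.2 | Section 6.3.2 | Synopsis |
|---|---|---|---|
| FD&C Blue No. 1 (brilliant blue) | named | named | named |
| Gelatin, porcine | named, as porcine proteins | absent | absent |
| P(EtOx-OH-NHS) polymer | covered as a component | absent | absent |
| P(EtOx-NH2) polymer | covered as a component | absent | absent |

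The granulate row of Table 1 consists of the two polymers, so there are 2 + 1 + 1 = 4 distinct raw materials. Section 2.3.2 names two hypersensitivities and covers all four materials in general terms. Sections 6.3.2 and the synopsis each name one hypersensitivity, which is 1 of 2 named and 1 of 4 materials.

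**Step 2. Follow a patient with known porcine-protein hypersensitivity through the listed rules**

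- Inclusion criteria (6.3.1): none concerns allergy.
- Hypersensitivity exclusion (6.3.2): not triggered, because the allergen is not the dye.
- Enrollment (6.3.4): satisfied if 6.3.1 and 6.3.2 are otherwise met.

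On the specific criteria, the patient qualifies.

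**Step 3. Look for other text that would stop treatment**

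- Section 2.3.2 itself. It names porcine proteins, but it is a device-level section on intended populations and is not one of the eligibility lists.
- Sections 6.4 and 6.4.5 allow use only where there are no contraindications. They list none, and the condition applies at the point of use in surgery.
- Table 4 schedules an allergy history at screening, and SAP section 8.3 says allergies go on the eCRF. This collects the information, but no listed criterion tells the site to exclude on a porcine entry.
- Section 6.3.2 lets the investigator exclude a subject judged unsuitable, or one with incidental findings that could endanger the patient. Neither item names an allergen, and an allergy already on record fits poorly as an incidental finding.

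**Step 4. How many subjects could be concerned**

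The planned maximum treated is 12 + 61 = 73. SAP section 5.1.1 reports that Stage I ended with 8 treated, so the attainable maximum is 8 + 61 = 69. The documents give no frequency of porcine-protein hypersensitivity, so the number of eligible carriers cannot be estimated and may be zero.

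**The case against.** The strongest reply is that the bar is already in the protocol. Section 2.3.2 is part of the clinical investigation plan, section 9.2 forbids deviations without prior approval except in emergencies, and waivers are prohibited. Read with 2.3.2, the condition on contraindications covers porcine hypersensitivity without leaving it to opinion. Allergy history and both discretion exclusions operate before surgery, so the problem can be caught in time. Section 4.4 also counts the instructions for use, training and follow-up among its risk controls. The instructions for use and the Investigator Brochure are not available here and may name porcine proteins. On this view the point is a minor inconsistency between two sections.

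Much of that stands. Treatment of such a patient should usually be prevented, and nothing suggests that the sponsor meant to admit one. The count of four materials describes wording and does not measure risk: the documents report no known hypersensitivity to the polymers.

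It does not remove the gap. The protection relies on a site connecting a device-description section with a general condition on use, when the eligibility list already contains a hypersensitivity item that appears complete. Section 9.2.1 treats departures from the inclusion and exclusion criteria as major deviations; treating this patient would breach no specific criterion and so might not be classed that way. It could also be said that 2.3.2 describes the eventual market and not the trial. But a bar meant for the marketed device should apply at least as firmly in a first-in-human study, and the trial already adopts the brilliant-blue half of it.

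**Conclusion.** The concern holds. The eligibility criteria admit, as written, a patient in whom the same protocol says the device should not be used. The omission is one named allergen from one criterion, appearing in two lists.

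The practical effect is probably small, because the other safeguards should normally stop treatment. Its size cannot be stated further without the allergen's frequency and the instructions for use. The mismatch itself is certain from the text; whether any subject is harmed is not. This is a safety and consistency matter that should be corrected. It has no bearing on the primary endpoint, the performance goal, sample size, power or type I error.

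**What to change.** Replace the hypersensitivity item in section 6.3.2 and in the synopsis with: *Known hypersensitivity to any material in the device, including porcine proteins (gelatin carrier) and brilliant blue (FD&C Blue No. 1).* Check at the same time that the contraindications in the instructions for use match.

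The cost is one phrase in two lists, plus the ethics committee and authority concurrence that section 9.1 requires for any amendment. No new data are needed, since allergies are already recorded, and at most a few subjects would be excluded. Stage I was complete when the SAP was written, so the change would protect only Stage II subjects not yet treated.
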